7.2.2. General Health Status/Quality of Life

PDQ-39 (Parkinson's Disease Questionnaire) (Appendix B) is a disease-specific, health-related quality-of-life assessment. It is a self-completed, patient-reported outcome (PRO) designed to address aspects of functioning and well-being for those affected by PD. Each of the 39 items is rated using a 5-point Likert scale, with 0 for never having difficulties/problems and 4 for always

having difficulties/problems. The sum score of the 39 items will be calculated and used for analysis, with the maximum score of 156 (Peto, 1998).

MoCA (Montreal Cognitive Assessment) (Appendix C) is a validated, 30-point, 1-page test administered by the PI or certified HCP designee and designed to assess several cognitive domains, including visuospatial abilities (5 points), naming (3 points), attention (6 points), language (3 points), abstraction (2 points), delayed recall (5 points), and orientation to time and place (6 points).

7.2.3. Treatment Satisfaction

TSQM-9 (Treatment Satisfaction Questionnaire for Medication) (Appendix E) is the abbreviated version of the original questionnaire (TSQM 1.4), a reliable and valid instrument with 14 questions to assess patients' satisfaction with medication. This PRO provides scores on four scales: side effects, effectiveness, convenience, and global satisfaction. Because questions relative to side effects could potentially interfere with patient care in a naturalistic setting, the 9 questions on effectiveness, convenience, and global satisfaction are often used without the 5 on side effects (Bharmal, 2009).

7.2.4. Global Impression

CGI-C (Clinical Global Impression – Change) (Appendix F) is a rating of the patient's overall improvement, based on a 7-point scale, using a range of responses from 1 (very much improved) through to 7 (very much worse) (Guy, 1976). The patient's improvement is rated by the PI/certified HCP designee.

PGI-C (Patient Global Impression – Change) (Appendix G) is a 7-point scale depicting a patient's rating of overall improvement. A patient reports his/her own change as "very much improved," "much improved," "minimally improved," "no change," "minimally worse," "much worse," or "very much worse" (Hurst, 2004).

8. CLINICAL INVESTIGATION PLAN

8.1. Study Design and Schedule of Assessments

This is a multisite, prospective, observational study to evaluate clinician-reported outcomes (ClinROs) and patient-reported outcomes (PROs) related to motor and non-motor symptoms, health status/QoL, and treatment satisfaction in a “real world” PD population in the US newly prescribed XADAGO in accordance with the Package Insert indication ([Appendix A](#)). The decision to prescribe XADAGO by clinician and patient must be made before site study staff discuss the study with the patient. If the patient is interested in participating in the study, an informed consent form (ICF) will be provided to the patient for review, contents of the ICF will be discussed, and patient’s signature will be obtained. Enrolled patients will be prospectively followed for 2 months, with the potential to participate in a 4-month Extension Study.

The Schedule of Assessments ([Table 3](#)) presents all the study activities that will occur at each study interaction with patients during clinic visits, by telephone at protocol-specified time points, and by PRO via the electronic Clinical Outcome Assessment (eCOA) system. Investigative sites will be provided secure access to 21 CFR Part 11-compliant electronic Case Report Forms (eCRF), and sites and patients will have access to the eCOA system(s) for collecting all patient data.

8.1.1. Screening / Baseline Assessments (Visit 1, Study Day 1)

The Screening Visit and the Baseline Assessment Visit may occur on the same day. During the Screening Visit, patients who provide written consent to participate in the study and HIPAA authorization to use their personal health information will be screened for inclusion in the study according to the following procedures:

- Assessment of eligibility criteria (i.e., Inclusion [[Section 9.1](#)] and Exclusion [[Section 9.2](#)] Criteria)
- Collection of demographics and medical history information, including history of PD and other neurological conditions

For patients determined to be eligible for the study, Baseline Assessments should be conducted at the same visit that Screening occurs. If the patient requires a separate Baseline Assessment Visit, it should occur no more than 7 days after the Screening Visit.

Patients will arrive at the Investigator’s clinic in an “on” motor state. The following activities and outcome assessments (Baseline Assessments) will be completed at the clinic Baseline Visit:

- Presentation of study instructions relative to XADAGO administration, concomitant medications, reporting of safety events, patient and Care Partner (if applicable), completion of CROs and PROs, downloading and training on the eCOA system, and documentation of other study data
- Registration and training on the eCOA system (in which the patient will report PRO results)
- Assessment of concomitant medications
- MDS-UPDRS by the PI/certified HCP designee

- PDQ-39 by the patient
- MoCA by the PI/certified HCP designee
- Study Day 1 administration of XADAGO

8.1.2. Telephone Follow-up with Patient by Study Site Staff (Visit 2, Study Day 30)

All patients will be contacted by telephone on Study Day 30. If the patient is scheduled for a routine clinic visit within ± 5 days of the Study Day 30 visit, the study assessments may be performed in person with the patient during the routine clinic visit.

The following assessments will be completed:

- Review of patient information relevant to XADAGO administration and concomitant medication administration
 - Daily record (e.g., electronic diary or log) will be available for the patient to enter information relevant to XADAGO and concomitant medications taken if patient decides to utilize
- PRO assessment:
 - TSQM-9

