6.2. XADAGO®

XADAGO (safinamide) is one of the newest treatments recently approved by the Food and Drug Administration (FDA) in the United States (US) as an add-on therapy to levodopa/carbidopa in patients with PD experiencing *off* episodes as described in the XADAGO Package Insert, May 2017 (Appendix A). XADAGO is an orally active, water-soluble, α -aminoamide derivative. It is a potent, selective, and reversible MAO-B inhibitor. In addition, the molecule safinamide has been shown in animal studies to exhibit state-dependent blockade of voltage-gated sodium channels, modulation of calcium channels, and subsequent inhibition of stimulated release of glutamate (Caccia, 2006; Caccia, 2007; Chazot, 2007; Pevarello, 1998; Stocchi, 2006) which may be implicated in the development of dyskinesia (Chase, 2003; Gregoire, 2013). The clinical implication of the activity is not known.

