7.2.1. Motor Symptoms and Non-Motor Symptoms

MDS-UPDRS (Appendix D) provides an assessment of the effects of PD on multiple aspects of a patient's life. The assessment is administered by the Principal Investigator (PI) or certified Health Care Professional (HCP) designee and consists of 4 parts:

- Part I focuses on non-motor experiences of daily living, such as mood, sleeping habits, pain, and fatigue. In IA, the investigator assesses various behaviors using information from the patient and caregiver; in IB, the assessments are completed by the patient without input from the investigator. Difficulties are rated on a 5-point scale, from 0=no problems to 4=severe problems.
- Part II is an evaluation of motor experiences of daily living, such as speech, eating, hygiene, and movement, and is completed by the patient. Difficulties are rated using the same 5-point scale as Part I.
- Part III assesses the severity of the cardinal motor findings (e.g., tremor, rigidity, bradykinesia, and postural instability). It includes 33 scores based on 18 items, and difficulties are rated using the same 5-point scale as Part I.
- Part IV is made up of questions on motor complications, and difficulties are rated using the same 5-point scale as Part I. This section integrates patient-derived information with the investigator's clinical observations and judgments and is completed by the rater (Goetz, 2008). It will be scored by the Investigator.

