8.1.3. Primary Endpoint Assessments (Visit 3, Study Day 60)

Patients will come to the study clinic for Primary Endpoint Assessments at Study Day 60.

The following assessments will be completed:

- Review of patient information relevant to XADAGO administration and concomitant medications administration
- Assessment of AEs
- Review of PRO completion compliance
- Clinical outcome assessments administered by the PI/certified HCP designee:
 - MDS-UPDRS
 - MoCA
 - CGI-C
- PRO assessments:
 - PDQ-39
 - TSQM-9
 - PGI-C

8.1.4. Follow-Up Study Assessments (Visit 4 [Study Day 90], Visit 6 [Study Day 180])

Patients will come to the study clinic on Study Days 90 and 180.

The following assessments will be completed:

- Review of patient information relevant to XADAGO administration and concomitant medications administration
- Assessment of AEs
- Review of PRO completion compliance
- Clinical outcome assessments administered by the PI/certified HCP designee:
 - MDS-UPDRS
 - MoCA (Visit 6 only)
 - CGI-C
- PRO assessments:
 - PDQ-39
 - TSQM-9
 - PGI-C

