9. SELECTION AND WITHDRAWAL OF PATIENTS

9.1. Inclusion Criteria

1. Patient (and Care Partner if required per Inclusion 7) is able to understand and provide signed informed consent and HIPAA authorization in English
2. Diagnosis of idiopathic PD (all stages)
3. Male or female, 30 to 80 years of age, inclusive, at initial screening assessment
4. Independent of the study, clinician's and patient's choice of treatment is XADAGO in accordance with the Package Insert indication ([Appendix A](#))
5. Patient is willing and able to participate in the study and complete study-related assessments for 2 months and, patients can continue for an optional 4-month study extension
6. Patient has access to an electronic device for the interim completion of PROs
7. Patient has an available Care Partner who is able and willing to assist with clinic attendance and completion of study assessments (e.g., PROs, health outcomes, etc.), if in the PI's opinion, assistance is needed to comply with all study visits and procedures

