##### **6.7.3. Change from Baseline**

Change from baseline is calculated as (post-baseline result – baseline result).

Percent change from baseline is calculated as (change from baseline/baseline result \* 100).

If either the baseline or the post-baseline result is missing, the change from baseline and/or percentage change from baseline is set to missing as well.

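### An *on* motor state is required on arrival at Baseline but at no later MDS-UPDRS visit, which can tilt the change scores toward worsening

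*Protocol*

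**What the plan says.** **Baseline.** Protocol 8.1.1 (Visit 1, Study Day 1): "Patients will arrive at the Investigator’s clinic in an “on” motor state". This is the only condition on motor state at assessment in either document.

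**Later visits.** Protocol 8.1.3: "Patients will come to the study clinic for Primary Endpoint Assessments at Study Day 60". Protocol 8.1.4: "Patients will come to the study clinic on Study Days 90 and 180". Both sections list the MDS-UPDRS, and neither mentions motor state. The schedules of assessments (Protocol Table 3, SAP Table 2) and their footnotes give no *on*/*off* condition and no timing relative to levodopa.

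**Population.** Protocol 6.2 describes the drug as approved "as an add-on therapy to levodopa/carbidopa in patients with PD experiencing *off* episodes". Inclusion criterion 4 ties enrolment to that use: "clinician's and patient's choice of treatment is XADAGO in accordance with the Package Insert indication".

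**Scale and analysis.** In the MDS-UPDRS a higher score is worse: "Difficulties are rated on a 5-point scale, from 0=no problems to 4=severe problems" (Protocol 7.2.1). Part III is the motor examination. SAP 6.7.3 takes change as follow-up minus baseline, so a positive change is worsening. SAP 8.4 applies a paired t-test to the change from Baseline to Day 60, with no term or rule for motor state. Protocol 12.5 names age, sex and disease duration as covariates, and SAP 8.2 plans no subgroups.

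**The concern.** The plan fixes motor state at one end of the primary change score and leaves it free at the other. Part III rates motor signs as they are at the visit, so its score depends on the state in which the patient is rated. In patients who have *off* episodes by indication, an *off* arrival at follow-up is foreseeable.

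Nothing in the design would absorb the difference. There is no randomisation and no comparator, so a difference in rating conditions between visits goes straight into the estimated change. The MDS-UPDRS is one of the three scales in the primary outcome analysis (Protocol 12.9.1). At stake is a mean change moved toward worsening, which could hide a real improvement or suggest a decline that did not occur.

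**Working it through.** The documents give no *off* share, no *off*-minus-*on* difference, no standard deviation (SD) of change and no power calculation. There is thus no stated figure to reproduce, and every value of f, D and SD below is an assumption.

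**1. Shift in the mean change.** Let f0 and f1 be the shares rated *off* at Baseline and at follow-up, and D the *off*-minus-*on* difference in points.

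Shift = (f1 − f0) × D

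If the shares are equal, the shift is 0, so the problem comes from the one-sided condition and not from *off* ratings as such. With f0 = 0, the shift toward worsening in points is:

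| f1 | D = 5 | D = 10 | D = 20 |
|---|---|---|---|
| 5% | 0.25 | 0.5 | 1.0 |
| 10% | 0.5 | 1.0 | 2.0 |
| 20% | 1.0 | 2.0 | 4.0 |

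If 5% were already *off* when rated at Baseline, 10% at follow-up with D = 10 would give (0.10 − 0.05) × 10 = 0.5 points in place of 1.0.

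**2. Added spread.** With f0 = 0 and f = f1, the mismatched pairs add f(1 − f)D² to the variance of change. For f = 10% and D = 10 this is 0.10 × 0.90 × 100 = 9.
- SD 8 becomes √(64 + 9) = 8.54.
- SD 12 becomes √(144 + 9) = 12.37.

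**3. Effect on the paired test.** Take a true change of 0, f = 10% and D = 10 (shift 1.0 point). The chance of a significant worsening is about Φ(shift/SE − 1.96), where SE is the standard error of the mean change. With no shift it is 2.5%.

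| n | SD of change | SE | Chance of false worsening |
|---|---|---|---|
| 540 | 8 | 8.54/√540 = 0.368 | 78% |
| 540 | 12 | 12.37/√540 = 0.532 | 47% |
| 180 | 8 | 8.54/√180 = 0.637 | 35% |
| 180 | 12 | 12.37/√180 = 0.922 | 19% |

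Here 540 is the planned maximum and 180 is an assumed equal third for one cohort. In the same case a true improvement of 1 point would be cancelled: −1.0 + 1.0 = 0. Over f = 5% to 30%, D = 5 to 15 and SD 8 or 12 at n = 540, the chance runs from 7% to nearly 100%. The documents do not say where in that range the study lies.

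**4. After the fix.** If ratings are made in the same state at each visit, f1 = f0 and the shift is 0. The sample size does not change.

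**The case against.** Several stronger readings are tempting, and the documents do not support them.

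- **A reader might infer that the error can only run toward worsening.** Section 8.1.1 governs arrival, not the moment of rating. Study instructions, eCOA registration and training, and the medication review are listed ahead of the MDS-UPDRS, and screening may fall on the same day. A patient can wear off before being rated, and an *off* baseline against an *on* follow-up would favour improvement. Only the net tendency toward worsening stands, provided *off* ratings are rarer at Baseline.
- **A reader might infer that some Day 60 ratings will be made *off*, or that following the plan produces unlike pairs.** The plan permits such pairs but does not require them. A site that rates every patient *on* at every visit also complies. The indication shows that patients have *off* episodes, not that they attend clinic in them.
- **A reader might infer that every within-patient change becomes noisier.** Same-state pairs are unaffected.
- **A reader might infer that motor state goes unrecorded.** The rating form is Protocol Appendix D, which is not in the text reviewed, so this cannot be checked. It can be said that the SAP makes no use of the state.

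It can also be argued that a real-world study should leave motor state free. That would be coherent if it were free at every visit; here it is fixed at one.

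Finally, restricting the main analysis to same-state pairs would bring its own bias. Protocol 6.2 reports that the drug reduced *off* time, so state at Day 60 may be affected by treatment. Dropping patients who are *off* at Day 60 could remove poorer responders and favour improvement. This objection stands and shapes the fix.

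**Conclusion.** The point holds as a foreseeable, avoidable asymmetry. Motor state is specified for arrival at Baseline and unspecified at Days 60, 90 and 180, and an uncontrolled paired analysis has no means of separating that difference from change. The expected direction is toward worsening, assuming *off* ratings are rarer at Baseline than later.

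The size is unknown. The range of 0.25 to 4 points rests wholly on assumed inputs, and its low end is negligible. The effect is clearest for Part III. It is less certain for Parts I and II, which ask about daily living, and for PDQ-39 and MoCA. This is a cheap improvement to the plan, not evidence that the results will be wrong.

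**What to change.** **Protocol 8.1.3 and 8.1.4.** Apply the motor-state condition already used at Baseline to the MDS-UPDRS at Days 60, 90 and 180. In these sections and in 8.1.1, word it to cover the state at the time of rating and not only on arrival.

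**Data capture.** Record the state at each MDS-UPDRS rating, unless the form in Appendix D already captures it.

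**SAP 8.4.** Keep all pairs as the main analysis. Add a sensitivity analysis of the Part III change in pairs rated in the same state, and note that state at Day 60 may be affected by treatment. SAP 8.4 does not name Part III separately, so the Part III change score has to be specified as well.

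**Cost.** A sentence in each of two protocol sections, a rewording in 8.1.1, possibly one eCRF field, and a short SAP addition with one extra table. The practical downside is that some visits will need timing within the day.

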8.2. Number of Patients

Up to 600 patients are planned for screening. This is expected to result in a final sample size of up to 540 eligible and evaluable enrolled patients, distributed among approximately 50 investigative sites in the US.

Table 3: Schedule of Assessments

Protocol Activity (Visit Type, Location, and Number; Study Day and Month; Window Allowance)	2-Month Main Study			4-Month Extension Study		
	Screening/Baseline Assessment Visit ^a	Follow-up	Primary Endpoint Visit	Follow-up	PRO Assessment Only	Follow-up
	Clinic	Telephone	Clinic	Clinic		Clinic
	Visit 1	Visit 2	Visit 3	Visit 4	Visit 5	Visit 6
	Day 1	Day 30	Day 60	Day 90	Day 120	Day 180
	Month 1		Month 2	Month 3	Month 4	Month 6
	±7 days	±2 days	±7 days	±7 days	±7 days	±14days
Informed Consent and HIPAA Authorization	X					
Eligibility: Inclusion/Exclusion Criteria	X					
Medical History and Demographics	X					
Medical History of PD, other Neurological Conditions	X					
Presentation of Study Instructions to Patient	X					
Registration and Training on eCOA System	X					
Concomitant Medications Assessment ^b	X	X	X	X		X
XADAGO Administration Compliance Review ^b		X	X	X		X
PRO Compliance Review ^b			X	X		X
Adverse Events Assessment ^b			X	X		X
MDS-UPDRS ^b	X		X	X		X
PDQ-39 ^c	X		X	X		X
MoCA ^b	X		X			X
TSQM-9 ^c		X	X	X	X	X
CGI-C ^b			X	X		X
PGI-C ^c			X	X		X

^a Screening will take place not more than 7 days before the Baseline Visit and may occur at the same time as the Baseline Visit. The first study dose of XADAGO will occur in the clinic on the Baseline Visit day, which will be designated Study Day 1.

^b Assessments to be administered by the PI/certified or HCP designee.

^c Assessments to be completed by the patient, with Care Partner assistance, if required.

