11.4. Recording Adverse Events

AEs spontaneously reported by the patient and/or in response to an open question from the study personnel or revealed by observation will be recorded during the study at the investigational site.

Information about AEs (and SAEs) will be collected from the time the patient signs the informed consent for this study and takes the first study dose of XADAGO until the patient’s last follow-up visit. The AE term should be reported in standard medical terminology when possible. For each AE, the investigator will evaluate and report the onset date, resolution date, intensity, causality, action taken, serious outcome (if applicable), and whether or not it caused the patient to discontinue the study.

Intensity will be assessed according to the following scale:

- Mild (awareness of sign or symptom, but easily tolerated)
- Moderate (discomfort sufficient to cause interference with normal activities)
- Severe (incapacitating, with inability to perform normal activities)

It is important to distinguish between serious and severe AEs. Severity is a measure of intensity whereas seriousness is defined by the criteria under Section 11.2.2. An AE of severe intensity may not be considered serious.

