##### **6.7.4. Visit Windows**

Visit windows were +/- 7 Days for Baseline, Visit 3, Visit 4 and Visit 5; +/- 2 Days for Visit 2 and +/-14 Days for Visit 6.

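### No adverse-event assessment is scheduled before Day 60, although staff contact every patient at Day 30, so early non-serious events may be under-counted or poorly dated

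*Protocol*

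**What the plan says.** Protocol 8.1.2 sets the Day 30 contact: "All patients will be contacted by telephone on Study Day 30". Its content is "Review of patient information relevant to XADAGO administration and concomitant medication administration", plus the TSQM-9. No AE item is listed.

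"Assessment of AEs" first appears in Protocol 8.1.3 (Visit 3, Day 60) and again in 8.1.4 (Days 90 and 180). In Protocol Table 3 the row "Adverse Events Assessment" is marked at Visits 3, 4 and 6 only, and SAP Table 2 has the same pattern. Neither table has an early-termination visit.

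The collection period is wider than the schedule. Protocol 11.4 says "Information about AEs (and SAEs) will be collected from the time the patient signs the informed consent", with first dose also required, and it runs to the last follow-up visit. The sources are "AEs spontaneously reported by the patient and/or in response to an open question from the study personnel", together with observation. These are not tied to particular visits.

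Protocol 9.4 requires a reason for every premature discontinuation. Patients who withdraw consent are asked why, so that an AE cause can be identified. Protocol 10.1.4 lets patients who stop XADAGO stay in the study.

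On the analysis side, Protocol 12.9.2 and SAP 9.2.1 report AEs by cohort and overall. SAP 9.2 counts a non-serious AE only if it occurs within 2 days of stopping treatment.

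**The concern.** Staff are already on the telephone with each patient at Day 30, discussing whether and how the drug is being taken. That conversation may reveal that a patient has stopped XADAGO, yet nothing in the schedule requires staff to ask whether anything untoward has happened. The TSQM-9 does not fill the gap, because Protocol 7.2.3 explains that this version omits the side-effect questions.

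Three things are at stake:

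- **Completeness.** A non-serious event that the patient does not volunteer has no scheduled prompt for about two months, and none at all if the patient leaves first.
- **Dating.** The SAP's 2-day counting rule depends on onset dates, which are harder to recall after a long interval. SAP 9.2.2 sends missing onset dates to SAP 6.8.1, which contains only last-observation-carried-forward for efficacy data, so a poorly recalled date has no working imputation rule.
- **Uniformity.** Protocol 11.4 permits an open question at any time but schedules none at Day 30. With roughly 50 sites (Protocol 8.2), some may ask and others may not. If sites differ in cohort mix, this feeds into the by-cohort AE tables.

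**Working it through.** The plan gives no figure for this point, so there is none to reproduce. The check is a comparison of passages followed by arithmetic on study days.

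**1. Do text and tables agree?**

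| Contact | Visit text lists AEs | Protocol Table 3 | SAP Table 2 |
|---|---|---|---|
| Day 1 | no | blank | blank |
| Day 30 | no | blank | blank |
| Day 60 | yes | X | X |
| Day 90 | yes | X | X |
| Day 120 | no (PRO only) | blank | blank |
| Day 180 | yes | X | X |

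They agree throughout, so the omission at Day 30 is neither a table-extraction fault nor an internal contradiction. Protocol 8.1 also says that Table 3 shows all activities at each interaction.

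**2. Interval from first dose to first scheduled AE assessment.** First dose is Day 1, so days since first dose = study day − 1. SAP 6.7.4 gives the windows: "Visit windows were +/- 7 Days for Baseline, Visit 3, Visit 4 and Visit 5", and plus or minus "2 Days for Visit 2".

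- Current plan: 60 − 1 = 59 days. The window is Days 53 to 67, giving 52 to 66 days.
- With an item at Visit 2: 30 − 1 = 29 days. The window is Days 28 to 32, giving 27 to 31 days.

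**3. Effect on dating, by example.** A patient stops XADAGO on Day 20 and stays in the study. The first scheduled AE question comes 60 − 20 = 40 days later. The analysis then has to judge whether an event began within 2 days of stopping. With a Day 30 item the delay is 30 − 20 = 10 days.

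**4. Patients who leave before Day 60.** The documents give no dropout rate, so 5%, 10% and 20% are assumptions, applied to the planned maximum of 540 enrolled.

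- 540 × 0.05 = 27
- 540 × 0.10 = 54
- 540 × 0.20 = 108

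These patients would have no scheduled AE assessment.

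**5. How many of them a Day 30 item would reach.** Assume exits spread evenly over Days 2 to 60, which is 59 days. Days 31 to 60 account for 30 of these, so the share is 30/59 = 0.508, about 51%.

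- 27 × 0.508 ≈ 14
- 54 × 0.508 ≈ 27
- 108 × 0.508 ≈ 55

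The share is lower if exits cluster early. The Day 30 item alone therefore solves about half of the early-leaver problem at best under this assumption, and the remainder needs a question at exit.

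**The case against.** A reader might infer that early leavers are never asked about AEs and that incidence will certainly be under-counted. The documents do not support that.

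- Protocol 9.4 requires patients who withdraw consent to be asked why, specifically to identify an AE cause. Patients removed for an intolerable AE are followed to resolution or stabilization. Under 11.4.2, those who discontinue because of an SAE are contacted 7 (±3) days later.
- AE collection under Protocol 11.4 is continuous, and Protocol 8.1.1 has patients instructed at baseline on reporting safety events. An AE mentioned during the Day 30 call must be recorded.
- Stopping XADAGO is not leaving the study. Patients who stop may stay and reach the Day 60 assessment.
- Reporting clocks (24 hours to record an SAE, 5 business days for a non-serious AE) start at observation or notification, not at a visit. Only events that nobody mentions are delayed.

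It can also be said that this is a deliberate design. The drug is marketed, Protocol 11.1 states that safety is not the principal objective, and the plan accepts a longer gap from Day 90 to Day 180. Finally, Protocol 8.2 describes the 540 as evaluable. If that means having a Day 60 MDS-UPDRS, none of those 540 left earlier, so the counts above apply only if 540 is read as enrolment, as in the synopsis.

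Most of this stands, and it limits the claim to what may happen. It does not remove the point. The withdrawal query seeks the reason for leaving, not all AEs, and cannot reach patients lost to follow-up. The 7-day contact covers only a known SAE. The later 90-day gap has no scheduled staff contact inside it, because Day 120 is a patient-completed questionnaire. At Day 30 the call is already made.

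**Conclusion.** The point holds in a limited form. No AE assessment is scheduled until Day 60, 59 days after first dose (52 to 66 with the window), although every patient is contacted at Day 30. Non-serious AEs in the first two months may be under-counted or imprecisely dated, and ascertainment may vary by site. The direction is reasoned from the schedule. The documents contain nothing from which the size of any under-count could be estimated.

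The shortening of the nominal first interval from 59 to 29 days follows directly from the schedule. The figures of 27 to 108 patients without a scheduled assessment, and 14 to 55 of them reached by a Day 30 item, rest on an assumed 5% to 20% loss before Day 60, on 540 enrolled, and on evenly spread exits. They are illustrations, not forecasts.

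The Day 60 outcome analyses of MDS-UPDRS, PDQ-39 and MoCA are unaffected, as is the reporting of any event once it is known. This is a cheap improvement to the safety tables and not a threat to the study's main results.

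**What to change.** 1. Mark "Adverse Events Assessment" at Visit 2 in Protocol Table 3 and in SAP Table 2.
2. Add "Assessment of AEs", asked as an open question, to the Day 30 list in Protocol 8.1.2.
3. In Protocol 9.4, have staff ask the same open question whenever the reason for early withdrawal is recorded. A Day 30 item cannot reach patients who leave before Day 30. Patients lost to follow-up would still be missed.

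The running cost is slightly longer calls and a few more AE entries. The edits also need a protocol amendment with IRB approval (Protocol 14.2). If patients have already passed Day 30 when it takes effect, AE ascertainment will differ before and after, and the report should say so.
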